2.1.2.1 COPD controller medication

At Screening Visit 1, all patients must be on triple background therapy, for 3 months prior to Visit 2/Randomization and at a stable dose of medication for at least 1 month prior to the Screening/Visit 1, including triple therapy: LABA + LAMA +ICS (Double therapy: LABA + LAMA allowed if ICS is contraindicated).

Throughout the study, patients should continue their established background therapy for COPD, including dose and regimen.

Patients must be willing to stay on their established background medication for COPD throughout the duration of the treatment period. After successful management of an acute exacerbation of COPD (eg, with oral corticosteroids and/or antibiotics), all efforts should be made to resume the initial background COPD treatment regimen if in the investigator's opinion this is medically acceptable. Background medications should not be adjusted during Screening. After 1 severe or 2 moderate exacerbations of COPD, dose adjustments in background therapy will be permitted for symptom control and as needed for the remainder of the trial period.

Adjustment of background medication is allowed at the discretion of the investigator as clinically indicated during the post-treatment period

2.1.2.2 Reliever medication

Patients may administer albuterol/salbutamol or levalbuterol/levosalbutamol or ipratropium or ipratropium/short-acting β agonists [SABA] combinations or terbutaline as needed during the study. Nebulizer solutions may be used as an alternative delivery method.

2.1.3 Efficacy endpoints

2.1.3.1 Primary efficacy endpoint

The primary endpoint for this study is the annualized rate of moderate or severe COPD exacerbation (as defined below) over the 52-week treatment period compared to placebo.

Moderate exacerbations are recorded by the Investigator and defined as AECOPD that require either systemic corticosteroids (such as intramuscular, intravenous or oral) and/or antibiotics.

Severe exacerbations are recorded by the Investigator and defined as AECOPD requiring hospitalization, or treatment for >24 hours in emergency department/urgent care facility or result in death.

For both moderate and severe events to be counted as separate events, they must be separated by at least 14 days.

The number of moderate or severe exacerbation events during the 52-week treatment period is defined as the number of moderate or severe exacerbation events with onset during the 52-week treatment period per patient-year. Patients who permanently discontinue the study medication will be asked and encouraged to return to the clinic for all remaining study visits and their additional off-treatment moderate or severe exacerbation events up to Visit 16 (Week 52) will be included.

AECOPD recorded in eCRF will go through a confirmatory adjudication by experts independent of sponsor for the evaluation. Details of the adjudication process are described in the AC Charter/Manual of Operation. Only the adjudicated confirmed AECOPD will be used for analysis.

2.1.3.2 Secondary efficacy endpoint(s)

The key secondary endpoints of this study include:

- Change in pre-bronchodilator FEV1 from baseline to Week 12
- Change in pre-bronchodilator FEV1 from baseline to Week 52
- Change in pre-bronchodilator FEV1 from baseline to Week 12 in the subgroup of patients with baseline FeNO \geq 20 ppb
- Change in pre-bronchodilator FEV1 from baseline to Week 52 in the subgroup of patients with baseline FeNO \geq 20 ppb
- Change from baseline to Week 52 in SGRQ total score
- Proportion of patients with SGRQ improvement \geq 4 points at Week 52
- Annualized rate of moderate or severe COPD exacerbation compared to placebo over the 52-week treatment period in the subgroup of patients with baseline FeNO \geq 20 ppb

Other secondary efficacy endpoints include:

- Change in pre-bronchodilator FEV1 from baseline through weeks other than 12 and 52 (ie, Weeks 2, 4, 8, 16, 20, 24, 28, 36, 44 and 48)
- Change in post-bronchodilator FEV1 from baseline to Weeks 2, 4, 8, 12, 24, 36 and 52
- Change in forced expiratory flow (FEF) 25-75% from baseline to Weeks 2, 4, 8, 12, 16, 24, 28, 36, 44, and 52
- Annualized rate of severe COPD exacerbations compared to placebo over the 52-week treatment period
- Time to first moderate or severe COPD exacerbation compared with placebo during the 52-week treatment period

2.1.3.2.1 Key secondary endpoint

2.1.3.2.1.1 Spirometry

Spirometry at clinical site visits should be performed in accordance with the European Respiratory Society (ERS)/American Thoracic Society (ATS) guidelines (1) and prior to administration of investigational product.

For pre-bronchodilator measured parameters, including FEV1, FVC and forced expiratory flow (FEF) 25%-75%, spirometry will be performed after a wash out period of bronchodilators according to their action duration, for example, withholding the last dose of salbutamol/albuterol or levalbuterol/levosalbutamol for at least 6 hours, withholding the last dose of LABA for at least 12 hours (ultra-long acting LABA like vilanterol should be withheld for at least 24 hours), withholding the last dose of ipratropium for at least 8 hours and withholding the last dose of LAMA for at least 24 hours. This will be verified before performing the measurements.

Note: When both pre- and post-bronchodilator spirometry is assessed, the post-bronchodilator spirometry should be performed consistent with the mechanism of action of reliever (ie, 30 minutes for albuterol or another SABA).

At all visits, spirometry will be performed preferably in the morning; afternoon/evening is allowable in the exceptional circumstance when morning spirometry cannot be performed; spirometry should be done at approximately the same time at each visit throughout the study. Current smokers need to be reminded not to smoke for at least 1 hour before spirometry. The same spirometer and standard spirometric techniques, including calibration, will be used to perform spirometry at all visits and, whenever possible, the same person should perform the measurements.

Three measurements fulfilling the ATS acceptability and repeatability criteria should be obtained at every visit, if possible.

2.1.3.2.1.2 St. George's Respiratory Questionnaire (SGRQ)

The St. George's Respiratory Questionnaire (SGRQ) (2, 3) is a 50-item questionnaire designed to measure and quantify health status in adult patients with chronic airflow limitation (see Appendix A).

Scores by dimension are calculated for three domains: Symptoms, Activity and Impacts (Psycho-social) as well as a total score. Global and domain scores range from 0 to 100, with 100 representing the worst possible health status and 0 indicating the best possible health status. See St. George's Respiratory Questionnaire manual Version 2.3 page 8-13 (Appendix C) for the scoring algorithm.

The first part ("Symptoms") evaluates symptomatology, including frequency and severity of cough, sputum production, wheeze, breathlessness and the duration and frequency of attacks of breathlessness or wheeze. The second part has two components: "Activity" and "Impacts". The "Activity" section addresses disturbances to patients' daily physical activities. The "Impacts" section covers a range of effects that chest troubles may have on patients' daily life and psycho-social functions (eg daily life activities and functioning, employment, physical functioning, emotional impact, stigmatization, and patients' perceptions when treated). The recall period of the questionnaire is over the past 4 weeks.

Psychometric testing has demonstrated its repeatability, reliability and validity. Sensitivity has been demonstrated in clinical trials. A minimum change in score of 4 units was established as clinically relevant after patient and clinician testing (4, 5). The SGRQ has been used in a range of disease groups including asthma, COPD and bronchiectasis.

SGRQ is assessed at Visit 2 (Week 0), Visit 4 (Week 4), Visit 6 (Week 12), Visit 9 (Week 24), Visit 12 (Week 36), Visit 16 (Week 52) and Visit 19 (Week 64).

2.1.3.2.2 *Exploratory/Tertiary efficacy endpoints*

2.1.3.2.2.1 Exacerbations of chronic pulmonary disease tool (EXACT)

The EXACT tool quantifies and measures exacerbations of COPD and assesses the symptomatic manifestations of these COPD exacerbations (see Appendix D). The instrument is a daily diary composed of a total of 14 items representing the following domains:

- Breathlessness (5 items),
- Cough and sputum (2 items),
- Chest symptoms (3 items),
- Difficulty bringing up sputum (1 item),
- Tired or weak (1 item),
- Sleep disturbance (1 item), and
- Scared or worried (1 item).

The EXACT total score assesses COPD exacerbations. The higher the score, the more severe are the symptoms.

The EXACT questionnaire is assessed daily from screening to Visit 16 (Week 52). Baseline EXACT score as well as the post-baseline weekly scores will be calculated as the mean within-patient score over the prior 7 days, with data present for a minimum of 4 of the 7 days. If fewer

than 4 days of data are available in the 7-day window, the EXACT score cannot be calculated and will be considered as missing. For the exacerbation analysis, the baseline would be reset during the study. Additional information related to computing scores and frequency, severity, and duration of events can be found in the user manual (6).

The Evaluating Respiratory Symptoms (E-RS) in COPD (E-RS: COPD) scale is a part of the EXACT tool. It is a derivative instrument used to measure the effect of treatment on the severity of respiratory symptoms in stable COPD. The E-RS utilizes the 11 respiratory symptom items contained in the 14-item EXACT.

The daily RS-Total score is computed by taking the sum of the 11 items comprising the instrument. It has a range of 0 to 40, with higher values indicating more severe respiratory symptoms.

The same summation procedure is used to derive the three daily domain scores:

- RS-Breathlessness (sum of items 7, 8, 9, 10, and 11; score range 0–17)
- RS-Cough and Sputum (sum of items 2, 3, 4; score range 0–11)
- RS-Chest Symptoms (sum of items 1, 5, 6; score range 0–12)

Like for EXACT, the baseline RS score as well as the post-baseline weekly domain and total scores are calculated as the mean within-patient score over the prior 7 days, with data present for a minimum of 4 of the 7 days. If fewer than 4 days of data are available in the 7-day window, the RS scores cannot be calculated and will be considered as missing.

2.1.4 Safety endpoints

The safety analysis will be based on the reported adverse events and other safety information, such as clinical laboratory data, vital signs, ECG and physical examination.

Observation period

The observation period will be divided into 4 epochs:

- The **screening** epoch is defined as the time from the signed informed consent date up to the time prior to first administration of the IMP.
- The **treatment** epoch is defined as the time from the first administration of the IMP to the last administration of the IMP + 14 days.
- The **residual treatment** epoch is defined as the time from the last administration of the IMP +15 days to the last administration of the IMP + 98 days.

The treatment-emergent adverse event period will include both **treatment** and **residual treatment** epochs.

- The **posttreatment** epoch is defined as the period of time starting the day after the end of the treatment-emergent adverse event period up to the end of the study (defined as last

protocol planned visit or the resolution/stabilization of all serious adverse events and adverse events with pre-specified monitoring).

- The on-study observation period is defined as the time from start of treatment until the end of the study (defined as last protocol planned visit or lost to follow-up or the resolution/stabilization of all serious adverse events and adverse events with pre-specified monitoring).

Safety events adjudication

Adjudication will be performed by experts independent of sponsor for the evaluation of whether deaths, cardiovascular SAEs and respiratory SAEs meet criteria for cardiovascular assessment endpoints. A confirmatory adjudication will occur for AECOPD exacerbations. Adjudicators will adjudicate these events in a consistent and unbiased manner throughout the study.

The goal of the adjudication is to ensure that all events reported by the site are judged uniformly, using pre-specified criteria by a group independent of the Sponsor. Adjudication Committee members will be blinded to treatment allocation. Adjudication Committee members' responsibilities and the process for data review are described in the AC Charter/Manual of Operation.

2.1.4.1 Adverse events variables

Adverse event observation period

- Pretreatment adverse events are adverse events that developed or worsened or became serious during the screening epoch
- Treatment-emergent adverse events are adverse events that developed or worsened or became serious during the treatment-emergent adverse event period
- Posttreatment adverse events are adverse events that developed or worsened or became serious during the posttreatment epoch

All adverse events (including serious adverse events and adverse events with pre-specified monitoring/of special interests) will be coded to a lower-level term (LLT), preferred term (PT), high-level term (HLT), high-level group term (HLGT), and associated primary system organ class (SOC) using the version of Medical Dictionary for Regulatory Activities (MedDRA) currently in effect at Sanofi at the time of database lock.

The occurrence of adverse events (including serious adverse events and adverse events with prespecified monitoring) will be recorded from the time of signed informed consent until the end of the study.

Cardiovascular assessment

All events submitted for cardiovascular adjudication will be listed and summarized, including the final classification results. A swimmer plot including all events classified as cardiovascular, including cardiovascular death, will also be provided.

Furthermore, events classified as cardiovascular will be evaluated according to the following composite endpoints:

- **Major Cardiovascular Adverse Events (MACE):** cardiovascular death, non-fatal myocardial infarction, or non-fatal stroke
- MACE + hospitalization for unstable angina
- Cardiovascular death: death resulting from myocardial infarction, stroke, pulmonary embolism, heart failure, procedure-related death or other cardiovascular cause.
- Hospitalization: for unstable angina, for atrial fibrillation/flutter, for other symptomatic arrhythmias, for transient ischemic attack.
- Other cardio/cerebrovascular events: non-fatal heart failure, peripheral arterial event, pulmonary embolism, non acute coronary syndrome/myocardial ischemia, others.

Adverse events of special interest (AESI) and other selected AE groupings will be searched based on the criteria in [Table 2](#).

Table 2 - Criteria for adverse events of special interest and other selected AE groupings

AE Grouping	Criteria
AESI	
Anaphylactic reaction	Anaphylactic reaction algorithmic approach (Introductory Guide for Standardised MedDRA Queries (SMQs) Version 18.1): includes anaphylactic reaction narrow SMQ (20000021) terms and programmatic identification of cases based on occurrence of at least two preferred terms meeting the algorithm criteria occurring within 24 hours of each other. The latter cases identified using the algorithm will undergo blinded medical review taking into account the timing of events relative to each other and to IMP administration for final determination of an anaphylactic reaction or not.
Hypersensitivity (medically reviewed)	SMQ hypersensitivity (20000214) narrow search or PT in (Pruritus, Pruritus generalized) and [AE corrective treatment/therapy='Y' or Action taken with IMP='Drug withdrawn' or Action taken with IMP='Drug interrupted'] followed by blinded medical review (documented process) for selection of relevant systemic hypersensitivity events
Serious injection site reactions or severe injection site reactions that last longer than 24 hours	HLT = 'Injection site reaction' and either with serious status, or with severe status and (AE end date/time - AE start date/time) ≥ 24 hours or ongoing
Severe or serious infection	Primary SOC = 'Infections and infestations' and with severe or serious status
Parasitic infection	The Infection Type 'Parasitic' was checked on eCRF page "Infection Defined as AESI Complementary Form"
Opportunistic infection	The Infection Type 'Opportunistic' was checked on eCRF page "Infection Defined as AESI Complementary Form"
Drug-related hepatic disorder	Drug-related hepatic disorders-Comprehensive search narrow SMQ (20000006)
Pregnancy	Primary SOC = 'Pregnancy, puerperium and perinatal conditions' or PT in (Aborted pregnancy, False negative pregnancy test, Pregnancy test positive, Pregnancy test urine positive, Ectopic pregnancy termination)
Symptomatic overdose with IMP	Symptomatic Overdose is answered Yes, with Overdose of IMP answered Yes on AE eCRF.
Symptomatic overdose with NIMP	Symptomatic Overdose is answered Yes, with Overdose of NIMP answered Yes on AE eCRF.
Eosinophilia	HLT = 'Eosinophilic disorders' or PT = 'Eosinophil count increased'
Other selected AE grouping	
Injection site reaction	HLT = 'Injection site reaction'
Malignancy	Sub-SMQ (20000091)– Malignant or unspecified tumors
Suicidal behavior	PT in (Completed suicide, Suicidal ideation, Depression suicidal, Suicidal behavior, Suicide attempt)

AE Grouping	Criteria
Partner pregnancy	PT in (Pregnancy of partner, Miscarriage of partner)
Conjunctivitis (narrow)	PT in (Conjunctivitis, Conjunctivitis allergic, Conjunctivitis bacterial, Conjunctivitis viral, Atopic keratoconjunctivitis)
Conjunctivitis (broad)	PT in (Conjunctivitis, Conjunctivitis allergic, Conjunctivitis bacterial, Conjunctivitis viral, Atopic keratoconjunctivitis, Blepharitis, Dry eye, Eye irritation, Eye pruritus, Lacrimation increased, Eye discharge, Foreign body sensation in eyes, Photophobia, Xerophthalmia, Ocular hyperaemia, Conjunctival hyperaemia)
Conjunctivitis (FDA)	PT in (Conjunctivitis, Conjunctivitis allergic, Conjunctivitis bacterial, Conjunctivitis viral, Eye irritation, Eye inflammation, Giant papillary conjunctivitis)

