#### **8.3.1 Adverse event of special interest**

An adverse event of special interest (AESI) is an AE (serious or nonserious) of scientific and medical concern specific to the Sponsor's product or program, for which ongoing monitoring and immediate notification by the Investigator to the Sponsor is required. Such events may require further investigation in order to characterize and understand them. Adverse events of special interest may be added, modified or removed during a study by protocol amendment.

For these AESIs, the Sponsor will be informed immediately (ie, within 24 hours), per SAE notification described in [Section 8.3.2](#), even if not fulfilling a seriousness criterion, using the corresponding pages in the CRF (to be sent) or screens in the e-CRF. If an SAE or any AESI of anaphylactic reactions or systemic allergic reactions that are related to IMP and require treatment, or severe injection site reactions lasting longer than 24 hours, occurs in a patient, blood samples should be collected for determination of functional dupilumab concentration, and ADA assessment at or near the onset and completion of the occurrence of the event, if possible (see [Section 8.5.1.3](#) for details).

- Clinically symptomatic eosinophilia (or eosinophilia associated with clinical symptoms)
- Anaphylactic reactions or systemic allergic reactions that are related to IMP and require treatment (see Appendix 15, [Section 10.15](#))
- Severe injection site reactions that last longer than 24 hours
- Any infection meeting at least one of the following criteria:
  - Any serious infection (SAE)
  - Requires parenteral (intravenous, intramuscular, subcutaneous) antimicrobial therapy

- Requires oral antimicrobial therapy for longer than 2 weeks
- Is a parasitic infection
- Is an opportunistic infection (see Appendix 16, [Section 10.16](#))

Note: antimicrobial therapy refers to antibiotic, antiviral, and antifungal agents

- Significant ALT elevation
  - ALT >5 x the upper limit of normal (ULN) in patients with baseline ALT  $\leq$  2 x ULN; or
  - ALT >8 x ULN if baseline ALT >2 x ULN
- Pregnancy of a female subject entered in a study as well as pregnancy occurring in a female partner of a male subject entered in a study with IMP/NIMP;

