Analysis of all treatment-emergent adverse event(s) leading to treatment discontinuation

- All treatment-emergent adverse events leading to treatment discontinuation, by primary SOC, HLG, HLT, and PT, showing the number (%) of patients sorted by the internationally agreed SOC order. The other levels (HLG, HLT, PT) will be presented in alphabetical order
- All treatment-emergent adverse events leading to permanent treatment discontinuation or drug interruption, by primary SOC and PT, showing number (%) of patients with at least one TEAE, will be presented by SOC internationally agreed order and by decreasing incidence of PTs within each SOC in the 300 q2w treatment group.

Analysis of Major Cardiovascular Adverse Events (MACE)

- The number and percentage (%) of patients with any treatment-emergent event selected for adjudication will be summarized by primary SOC and PT.
- All events submitted for adjudication will be listed, including the final adjudicated result.
- The number and percentage (%) of patients experiencing a treatment-emergent adjudicated event will be summarized within each treatment group.

- The risk difference (asymptotic 95% CI with continuity correction) will be computed for the dupilumab dose versus placebo. Kaplan-Meier plots to depict the course of onset over time will also be provided.

Analysis of adverse events of special interests (AESI) and other selected AE groupings

- All treatment-emergent adverse events, by selected standardized MedDRA query (SMQ) and PT or by laboratory values (as in ALT elevation), showing the number (%) of patients with at least 1 PT, sorted by decreasing incidence of PTs within each SMQ in the 300 q2w treatment group.
- For each AESI and other selected AE groupings,
 - Number (%) of patients with any specific TEAE
 - Number (%) of patients with any specific serious AE (regardless of treatment emergent status)
 - Number (%) of patients with any specific treatment emergent serious AE
 - Number (%) of patients with any specific AE leading to death
 - Number (%) of patients with any specific TEAE leading to permanent study drug discontinuation
 - Number (%) of patients with any specific TEAE related to IMP reported by investigator
 - Number (%) of patients with any specific TEAE by maximum intensity, corrective treatment, and final outcome
 - Number of any specific TEAE adjusted by the exposure duration

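### SAP Table 2 has no group for two of the protocol's five infection AESI criteria, and it does not define the laboratory-value ALT group to which SAP 2.4.5.1 refers

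*SAP*

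**What the plan says.** **Protocol, infection.** Section 8.3.1 counts an infection as an AESI if it meets at least one of five criteria. It is serious ("Any serious infection (SAE"), or it "Requires parenteral (intravenous, intramuscular, subcutaneous) antimicrobial therapy", or it "Requires oral antimicrobial therapy for longer than 2 weeks", or it "Is a parasitic infection", or it "Is an opportunistic infection".

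**Protocol, ALT.** The same section defines significant ALT elevation by measured value: above 5 x ULN when baseline ALT is at most 2 x ULN, and above 8 x ULN when baseline is higher than that.

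**Protocol, analysis.** Table 10 (section 9.4.2) asks for a set of summaries for each type of AESI. These include patients per 100 patient-years, intensity, corrective treatment, outcome and Kaplan-Meier estimates. It leaves the method of identifying AESIs to the SAP.

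**SAP, identification.** Section 2.1.4.1 says that AESIs are searched for with the criteria in Table 2. The main infection row reads "Primary SOC = 'Infections and infestations' and with severe or serious status". Two further rows take parasitic and opportunistic infections from a tick-box on the infection AESI eCRF form. The only liver row is a search of coded terms (it reads "Drug-related hepatic disorders-Comprehensive search narrow SMQ (20000006").

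**SAP, analysis.** Section 2.4.5.1 displays AESIs by coded terms or laboratory values (in its words, "by selected standardized MedDRA query (SMQ) and PT or by laboratory values (as in ALT elevation"). It then lists the detailed summaries for each AESI and each other grouping, and adds that AESIs reported by the investigator will be summarized separately.

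**The concern.** Table 2 decides which events enter the detailed per-AESI outputs. If it leaves out part of what the protocol calls an AESI, those outputs describe a different set of events from the one the protocol singled out for immediate notification and special analysis.

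For infection, the part left out is the class defined by how intensively the infection had to be treated. In a trial of an immunomodulator this class deserves complete, pre-specified reporting by arm. For ALT, a programmer working from the SAP cannot build the laboratory-value group that section 2.4.5.1 mentions, because no cut-off is given for it.

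**Working it through.** No figure in the plan depends on this point, so there is nothing to reproduce. The check sets the definitions side by side.

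| Protocol 8.3.1 criterion | Row in SAP Table 2 |
|---|---|
| Serious infection | Yes (severe or serious row) |
| Parenteral antimicrobial therapy | None |
| Oral antimicrobial therapy for more than 2 weeks | None |
| Parasitic | Yes (eCRF tick-box) |
| Opportunistic | Yes (eCRF tick-box) |
| Severe: not a protocol criterion | Added by the SAP |
| ALT above 5 x ULN, or above 8 x ULN if baseline exceeds 2 x ULN | None; coded-term search only |

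**Infection, by enumeration.** Describe an infection by six yes/no features: serious, severe, parenteral therapy, oral therapy over 2 weeks, parasitic, opportunistic. Assume it is coded to the infections SOC. There are 2^6 = 64 profiles.

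- Protocol rule: a profile is not an AESI only when all five protocol features are absent. Severity is then free, which gives 2 profiles, so 64 - 2 = 62 are AESIs.
- Table 2 rule: a profile is outside the three rows only when serious, severe, parasitic and opportunistic are all absent. The two therapy features are then free, which gives 4 profiles, so 64 - 4 = 60 are captured.
- Protocol AESIs outside Table 2: 3 profiles (parenteral only, prolonged oral only, both).
- In Table 2 but not protocol AESIs: 1 profile (severe only).
- Cross-check: 62 - 3 + 1 = 60.

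These are counts of profiles, not of patients. Table 2 covers three of the five protocol criteria.

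**Where the three missed profiles still appear.** SAP 2.4.5.1 puts them in the all-TEAE tables by SOC and preferred term and by maximal severity. If the investigator flags them, they are also in the separate AESI summary. The SAP does not say whether that summary includes exposure adjustment, intensity, outcome or Kaplan-Meier estimates.

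**ALT.** SAP Appendix A tabulates ALT above 3, 5, 10 and 20 x ULN. Both protocol thresholds (5 and 8) are at or above 5, so every protocol ALT event observed in the treatment-emergent period is counted in the above-5 row. That row also takes in patients with baseline above 2 x ULN and a peak above 5 and up to 8 x ULN, who are not protocol AESIs. Exclusion E 38 keeps out screening ALT above 3 x ULN, so this group is mainly patients with baseline of about 2 to 3 x ULN. The laboratory Kaplan-Meier analysis in SAP 2.4.5.3 uses 3 x ULN. No SAP output uses the protocol's baseline-dependent rule.

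**Size.** The documents give no infection incidence. Under purely assumed rates, with 5% of patients captured and a further 1% to 5% missed, the share missed would be 1/(5+1) = 17% to 5/(5+5) = 50%. That span comes entirely from the assumed inputs and is not an estimate.

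**The case against.** **The protocol supplied may not govern the SAP.** SAP 1.5 works from protocol amendment 7, and lists the EXACT wording as the only change from it. Yet the supplied protocol has two primary endpoints where the SAP has one, stratifies in section 6.3.1 by asthma history where the SAP uses high-dose ICS, and defines severe exacerbation differently. Protocol 8.3.1 also allows AESIs to be changed by amendment. This stands. A reader might infer that the SAP narrowed the definition in force, but the documents do not establish that, so the amendment must be checked first.

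**The SAP was given the task of identifying AESIs.** It was, in Table 10. That covers the method of finding events; it does not obviously cover dropping two criteria. If the definition is unchanged, SAP 1.5 should have recorded the departure.

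**The events are still reported.** This also stands. A reader might infer that the infections vanish from the study report. They do not: they miss only the detailed per-AESI summaries. Nor is a formal comparison lost, because SAP 2.4.5 makes safety essentially descriptive and SAP 2.4.5.1 makes the per-AESI Kaplan-Meier output conditional on enough events.

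**ALT events are not lost.** A reader might infer that they drop out because Table 2 searches coded terms only. The documents do not support that, given the above-5 x ULN row and the laboratory-value display foreseen in SAP 2.4.5.1. Whether the coded-term search picks up reported ALT increases depends on query content that the documents do not give.

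**The data may not allow the missing rows.** This stands in part. Protocol 6.5 lists reason, dates, dose and frequency for concomitant medication, but not route. SAP 2.5.3 does not impute medication dates. Table 2 shows only the infection-type field of the AESI form.

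**Conclusion.** On the texts supplied, the infection gap is real. Two of the five protocol criteria have no Table 2 group, and infections that qualify only through them are left to general tables and a summary of unspecified content. Table 2 also adds severe infections, which the protocol does not list; that broadens the group and does no harm as long as the protocol set can be shown separately.

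The ALT point is smaller. A group is referred to but not defined, and the protocol's baseline-dependent rule is never applied.

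This concerns the completeness of safety reporting. The number of events affected cannot be estimated from the documents, and no efficacy result depends on it. The infection conclusion, and the statement about the protocol's ALT rule, assume that the AESI definitions in amendment 7 match those in the supplied protocol. The missing ALT cut-off lies within the SAP and stands either way.

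**What to change.** 1. Check the AESI definitions in the protocol version that governs the SAP (amendment 7).
2. If the infection definition is unchanged, add to Table 2 a row *Any protocol-defined infection AESI* that unites all five criteria, including the two antimicrobial-therapy ones. Identify these from the investigator-reported infection AESI form, or from concomitant medication if route and dates allow, and state which source is used.
3. Add a row *Significant ALT elevation*, identified by laboratory value with the protocol's own thresholds, so that the reference in SAP 2.4.5.1 has a definition.
4. Keep the existing rows and run the SAP 2.4.5.1 summaries on the new ones.
5. If the sponsor prefers the present grouping, record and justify the departure in SAP 1.5.

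The cost is some Table 2 wording and a few more safety tables, plus confirmation that the eCRF can identify the two therapy criteria. Reported infection AESI incidence may rise somewhat in both arms. Alpha, power and sample size do not change.
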